TITLE	Effectiveness of nonspecific methods of treatment and Zopiclone for chronic insomnia
SPONSOR	
FUNDING ORGANIZATION	
NUMBER OF SITES	
RATIONALE	Importance of chronic insomnia (CI) problem is determined by its high prevalence rate, comorbidity and resistance to the treatment. There are pharmacological and cognitive-behavioral approaches to the CI treatment. Even after considering all the specific advantages and drawbacks of both methods of CI treatment a clinician would be still in question, which one would be preferable in a particular case.
STUDY DESIGN	Prospective randomized crossover study
PRIMARY OBJECTIVE	to test the effectiveness of short BBT-I program for chronic insomnia in comparison with zopiclone
SECONDARY OBJECTIVES	to find anthropometric, psychological and polysomnographic predictors of effectiveness of each method
NUMBER OF SUBJECTS	
SUBJECT SELECTION CRITERIA	
Inclusion Criteria: meeting the criteria for chronic insomnia according ICSD-3 willingness to take part in the study and signed informed consent form
 
Exclusion Criteria: (1) inability to stop taking medications that have a proven impact on sleep at least one week before and during the study; (2) history of alcohol or drug abuse; (3) major depressive disorder or other severe mental disorder identified by a clinical assessment and medical history; (4) dementia; (5) pregnancy or lactation; (6) shift or night work; (7) medical problems that would be a direct cause of sleep complaints: moderate/severe sleep apnea, defined as an apnea–hypopnea index of ≥ 15 events per hour, periodic limb movement disorder defined as a periodic leg movement index ≥ 15 events per hour or restless legs syndrome; (8) other serious chronic conditions or exacerbation of chronic disorder preventing further participation.

TEST PRODUCT, DOSE, AND ROUTE OF ADMINISTRATION	
2-week Brief behavioral therapy program includes a question-and-answer part; a didactic presentation of sleep regulation mechanisms; an examination of patient's sleep log; explanation of sleep restriction method and prescription of individual regimen of sleep; explanation of stimulus control method; sleep hygiene education; discussion of relaxation techniques, providing with relaxation audio recording.
 
BBT-I first group Will receive two-week brief behavioral therapy followed by medication therapy (zopiclone).

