The main treatment approaches for chronic insomnia with proven efficacy are pharmacologic and behavioral treatment. In accordance with the results of multiple clinical trials and meta-analyses both methods have comparable effectiveness in terms of sleep quality ranging between 64% (Buysse et.al., 2011) and 88% (Carson, McDonagh, Thakurta, and Yen P. 2008).

GABA(a) agonists being the most widely used hypnotics could cause residual daytime sedation and safety concerns like the risk of drug addiction, overdose and intoxication along with cognitive toxicity, falls and hip fractures especially in elderly persons (Pagel & Parnes, 2001)

The second approved treatment option for insomnia is cognitive-behavioral treatment of insomnia combining behavioral and psychological techniques. Unlike hypnotics this method has consistent long-term efficacy with few adverse effects (Morin et.al., 2016). On the other hand it requires special training of therapist, compliance of patient and noticeable time expenditures of both. Hence shortened and simplified behavioral approaches have been developed. It includes brief behavioral treatment for insomnia (BBT-I) lasting four weekly sessions instead of 6-8, online sessions, telephone consultations, and self-help approaches. Although there are not enough data for meta-analysis, BBT-I proved its efficacy in a number of clinical comparative studies (Bootzin, 2004).

STUDY RATIONALE

Even after considering all the specific advantages and drawbacks of pharmacological and cognitive-behavioral methods of CI treatment a clinician would be still in question, which one would be preferable in a particular case. There are still questions about the reason why CBT or pharmacotherapy or even their combination didn't reach 100% treatment response. So the treatment response predictors identification is required for individualized treatment

Risk / Benefit Assessment

Brief behavioral therapy has no potential adverse effects, risks of addiction or tolerance.

Zopiclone has possible hypersensitivity adverse effects as well as possible effects on central nervous system: taste disturbance; less commonly nausea, vomiting, dizziness, drowsiness, dry mouth, headache; rarely amnesia, confusion, depression, hallucinations, nightmares; very rarely light headedness, incoordination, paradoxical effects. Nevertheless it remains medication recommended for insomnia treatment in accordance with international guidelines

STUDY OBJECTIVES

Primary Objective

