To test the effectiveness of short BBT-I program for chronic insomnia in comparison with zopiclone in Russian population.

Secondary Objectives

Identification of anthropometric, psychological and polysomnographic predictors of effectiveness of each method.

STUDY DESIGN

Study Overview

Prospective randomized crossover study. In accordance with this design every patient will receive two different treatment courses in random sequence: zopiclone or structured educational program (BBT-I) delivered in two sessions. Patients of the zopiclone-first group will receive the medication therapy for the first two weeks followed by educational program. Patients of the BBT-I-first group will receive two-week educational program followed by medication therapy.

Each treatment course will be separated by 2-weeks washout period that will provide the opportunity to evaluate the sustainability of treatment effect.

The total duration of the study will be 8 weeks with 6 visits including 1 night polysomnography (PSG), 2 face-to-face structured educational program sessions and 5 diagnostic interviews. Total duration of the study will be 2 years.

Criteria for evaluation

Primary Efficacy Endpoint

Proposed primary efficacy endpoint is change of insomnia severity index (ISI) after treatment. Criterion of response to the treatment will be defined as the reduction of ISI score reduction of >7 points from baseline. This criterion is indicative of moderate improvement and validated as clinically significant (Morin, Belleville & Belanger, 2011). Remission criterion will be defined as final

ISI score of 7 points or less. Nonresponse criterion will be defined as ISI score decrease of ≤ 7 points from baseline.

Secondary Efficacy Endpoints

1. Insomnia severity index self reported insomnia symptoms severity . Each item is scored 0 (no problem) - 4 (very big problem) with total between 0-28 (absence of insomnia (0-7); sub-threshold insomnia (8-14); moderate insomnia (15-21); and severe insomnia (22-28).
2. Beck Depression Inventory. 21-item questionnaire assessing (on 4-point Likert scales) the intensity of depressive symptoms in the past week
3. State-trait anxiety inventory. 2-part questionnaire assessing state (situational) and trait anxiety. Both situational and trait parts comprise 20 items rated on a 4-point Likert scale.
4. Dysfunctional beliefs about sleep scale. questionnaire assessing sleep related cognitions in 16 item rated on a 10-point Likert scale.

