Subjects withdrawn from the study treatment will be replaced. Subjects withdrawn from the study after Visit 5 but prior to Visit 6 won't be replaced.

Protocol Violations

Protocol violations for this study include, but are not limited to, the following:

- Failure to meet inclusion/exclusion criteria

- Use of a prohibited concomitant medication
- Non-compliance with study drug regimen, and questionnaires completion

Failure to comply with Good Clinical Practice (GCP) guidelines will also result in a protocol violation. If a protocol violation occurs, a Protocol Violation Form detailing the violation will be generated.

DATA SAFETY MONITORING

There will be no data monitoring committee

STATISTICAL METHODS AND CONSIDERATIONS

A Statistical Analysis Plan (SAP) is written describing all analyses that will be performed.

Data Sets Analyzed

All subjects matching inclusion and exclusion criteria who will complete at least one treatment course (BBT-I or medication) and fill in questionnaires prior and after the treatment will be included in the safety analysis.

Demographic and Baseline Characteristics

The following demographic variables at screening will be summarized by dose level: gender, age, height and weight. Continuous variables will be presented in means and standard deviation ($M \pm SD$).

Analysis of Primary Endpoint

Statistical significance of differences between ISI level before and after treatment for both treatment methods will be evaluated with Student's t-test after confirmation of normal variable distribution by Kolmogorov-Smirnov test. For continuous variables with distribution other than normal Mann-Whitney U-test will be used. For comparison of the proportions Pearson chi-squared test will be performed.

Criterion of response to the treatment is defined as the reduction of ISI score reduction of >7 points from baseline. This criterion is indicative of moderate improvement and validated as clinically significant (Morin, Belleville & Belanger, 2011). As well the criterion corresponds to approximately 1 standard deviation of the pretreatment values (Cohen effect size of approximately 1.0). Remission criterion is defined as final ISI score of 7 points or less. Nonresponse criterion is defined as ISI score decrease of ≤ 7 points from baseline.

Analysis of Secondary Endpoints

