Statistical significance of differences between BDI, STAI, PSQI, DBAS, SHI, β -adrenoreactivity level, sleep diary data before and after treatment for both treatment methods will be evaluated with Student's t-test after confirmation of normal variable distribution by Kolmogorov-Smirnov test. For continuous variables with distribution

other than normal Mann-Whitney U-test will be used. For comparison of the proportions Pearson chi-squared test will be performed.

Based on the response criterion participants will be divided into two groups: responders and nonresponders for each method of treatment. Comparison of responders and nonresponders baseline quantitative characteristics (polysomnographic, antropometric, psychometric) will be performed using Student's t-test (for normal data distribution) or Mann-Whitney U-test (for abnormal data distribution). Statistical significance will be set at a p-value less 0,05.

Safety and tolerability data will be summarized by treatment group. Adverse events will be tabulated by treatment group and include the number of patients for whom the event occurred, the rate of occurrence, and the severity and relationship to study drug.

Interim Analysis

Interim statistical analysis will be performed after 20 patients complete the study protocol.

Sample Size and Randomization

The number of subjects planned to be enrolled is 40. This is a representative sample for study of treatment effects. The crossover design of the study will allow us to compare two therapeutic approaches with a relatively small sample size and to determine the predictors of effectiveness for each treatment.

DATA COLLECTION, RETENTION AND MONITORING

Data Collection Instruments

The Investigator will prepare and maintain adequate and accurate source documents designed to record all observations and other pertinent data for each study subject. The information corresponding to each visit will be entered to the study database and to paper CRF.

The Investigator is responsible for all information collected on subjects enrolled in this study. All data collected during the course of this study will be reviewed and verified for completeness and accuracy by the Investigator.

Data Management Procedures

The data will be entered into a validated database. The Investigator is responsible for data processing, in accordance with procedural documentation.

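### The predictor analysis tests each method separately, so it cannot tell a general prognostic factor from one that favours BBT-I or zopiclone, which is the choice the rationale asks about

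*Combined protocol and SAP*

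**What the plan says.** The synopsis rationale and the Study Rationale section give the clinical question: after weighing both approaches, "a clinician would be still in question, which one would be preferable in a particular case". The Study Rationale then draws the link to predictors: "So the treatment response predictors identification is required for individualized treatment". The secondary objective is worded more narrowly: "Identification of anthropometric, psychological and polysomnographic predictors of effectiveness of each method".

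The analysis is in Analysis of Secondary Endpoints, and the synopsis (Primary Analysis Plan) repeats it in substance. Response is defined on the ISI: "Criterion of response to the treatment is defined as the reduction of ISI score reduction of >7 points from baseline". On that definition, "Based on the response criterion participants will be divided into two groups: responders and nonresponders for each method of treatment". The test follows: "Comparison of responders and nonresponders baseline quantitative characteristics (polysomnographic, antropometric, psychometric) will be performed using Student's t-test", with Mann-Whitney for non-normal data. The threshold is given as "Statistical significance will be set at a p-value less 0,05".

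Neither place contains a term for method by characteristic, a model holding both methods, or an analysis of each patient's difference between methods. Study Overview says that each patient has both courses in random order. Sample Size and Randomization credits the crossover with making it possible to find predictors for each treatment.

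**The concern.** To choose between two treatments for a patient, one needs evidence that a characteristic's relation to outcome differs between them. Two separate sets of tests do not give that evidence:

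- A factor significant on both methods may be purely prognostic and need not guide the choice.
- A factor significant on one method and not on the other has not been shown to differ between them. At this sample size, one hit and one miss is a common result even when the two relations are identical.

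The plan would yield two lists of factors with p below 0.05. Given the stated rationale, a factor on one list only is easily taken as a reason to prefer that method, and the analysis cannot support that step. The pairing of results within patients, which could address it directly, is not used.

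**Working it through.** **No planned figure to reproduce.** The sample size of 40 comes with no effect size, SD or power. The check therefore asks how the planned pair of tests behaves at N = 40.

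**Precision of one within-method test.** The detectable difference at 80% power and two-sided 0.05 (sidedness is not stated, so assumed) is (1.960 + 0.842) × √(1/n₁ + 1/n₀) baseline SDs:

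- 20 responders, 20 nonresponders: 2.802 × 0.316 = 0.89 SD
- 26 and 14: 0.93 SD
- 30 and 10: 1.02 SD

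Only large differences are found reliably, so a real factor will often be found on one method and missed on the other.

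**Simulation model.** From the documents: 40 patients, both methods in each patient, a responder split within each method, a t-test at 0.05. Assumed: correlation *r* of a baseline factor with ISI change under each method; residual correlation ρ between a patient's two changes; response rates; no period effect; no carry-over except where stated. The response rates tried were 50%/50% and 65%/50% (ρ 0 to 0.5), and 64% and 88% (ρ 0.4). The 64% and 88% appear in Overview of Clinical Studies as literature figures for sleep quality. They are used here only as assumed response rates.

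The direct test regresses the within-patient difference in ISI change on the factor.

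**A factor with the same *r* on both methods.** P(exactly one significant) = P(zopiclone) + P(BBT-I) − 2 × P(both). Three of the settings:

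- *r* 0.3, ρ 0, 50%/50%: 0.320 + 0.321 − 2 × 0.105 = 0.43
- *r* 0.4, ρ 0, 65%/50%: 0.511 + 0.539 − 2 × 0.281 = 0.49
- *r* 0.5, ρ 0.5, 50%/50%: 0.759 + 0.755 − 2 × 0.612 = 0.29

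The lowest value, about 27%, arises at 88% response, *r* 0.3 and ρ 0.4. Across all settings with *r* from 0.3 to 0.5 the range is roughly 27% to 49%. The direct test rejects in about 5% throughout.

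**A factor unrelated to change on either method.** About 9% to 10% of such factors are significant on exactly one method; independence would give 2 × 0.05 × 0.95 = 9.5%. The direct test gives 5%.

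**A factor that truly differs between methods** (assumed 64% response, ρ 0 to 0.4):

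| *r* on the two methods | Planned separate test | Direct test of difference |
|---|---|---|
| +0.3 / −0.3 | about 31% on each method | 76–92% |
| 0.4 / 0 | about 51% on the first | 42–61% |
| 0.5 / 0.2 | 73% on the first | 28–43% |

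The direct test has clearly more power in the first row, about the same in the second and less in the third. The two columns also answer different questions: the separate test asks whether the factor matters on one method, the direct test whether it matters differently.

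**Carry-over.** Suppose that part of each patient's BBT-I gain reduces the later change on zopiclone in the BBT-I-first group. For a purely prognostic factor with *r* 0.5, the direct test's false-positive rate rises from about 5% to about 10% at 50% carry-over and 14% at 70% (both assumed). A sequence term does not remove this, because it adjusts the mean and not the factor's slope.

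**The case against.** The strongest reply is that the written objective asks for predictors for each method, and the planned comparisons address that literally. No section states that a factor on one list only differs between methods. A reader might infer that the secondary objective goes unanswered; the documents do not support that. The gap is between the analysis and the rationale, and restricting conclusions to within-method association would also close it.

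A reader might also infer that the planned tests only find people who would improve on any treatment. That goes too far. A within-method comparison can pick up a general factor, a method-specific one, or natural course and regression to the mean, as there is no untreated arm. Its limit is that it cannot tell them apart.

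A third tempting reading is that the direct test is simply more powerful. The large gain belongs to a factor with opposite signs on the two methods, and the advantage can reverse. Part of it comes from using ISI change as a continuous outcome: at *r* 0.3, a continuous within-method test has 48% power against 31% for the responder split.

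Finally, the direct test has limits in this trial. Overview of Clinical Studies credits cognitive-behavioural treatment with lasting benefit, and Study Overview uses the washout partly to see whether effects persist, so carry-over is plausible. The plan does not say whether baseline for the second course is Visit 1 or Visit 3, which changes who counts as a responder. The synopsis admits patients who complete one course, and they have no within-patient difference.

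All of this stands. It narrows the claim and shapes the remedy, but it does not make two separate tests informative about the choice between methods.

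**Conclusion.** The point holds as a limit on what the predictor analysis can show. Separate responder comparisons cannot separate general prognosis from an advantage of one method, and the rationale asks "which one would be preferable in a particular case". At N = 40, a factor with identical relations to improvement on both methods would look method-specific in roughly 27% to 49% of trials, against about 5% for a direct test. These figures rest on assumed correlations of 0.3 to 0.5, the assumed response rates and residual correlations listed above, and no carry-over. With substantial BBT-I carry-over related to the factor, the direct test's error could reach 10% to 14%, so it needs a sensitivity analysis beside it. The case for the change is validity, not a general gain in power.

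**What to change.** In Analysis of Secondary Endpoints, and to match in the synopsis:

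1. For each baseline factor, add a method-by-factor test. Either fit a mixed model of ISI change during each course with method, period, factor and method-by-factor terms, which keeps one-course patients, or, for complete pairs, regress the within-patient difference in ISI change on the factor with a sequence term.
2. State which visit is the baseline for the second course.
3. Claim that a factor helps to choose between methods only if this test supports it. Keep the by-method responder comparisons as descriptive within-method associations.
4. Add a first-period-only method-by-factor analysis as a sensitivity check against BBT-I carry-over. It compares different patients in the two sequences and will be imprecise.
5. Label all predictor results exploratory at N = 40.

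The cost is SAP wording and a small number of models per factor, with no new data and no more patients. The downside is that some factors that would have looked method-specific will not be claimed.

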
STATISTICS Primary Analysis Plan
	
Analysis of insomnia treatment will be conducted only for patients matching inclusion and exclusion criteria who will complete at least one treatment course (BBT-I or medication) and fill in questionnaires prior and after the treatment. Continuous variables will be presented in means and standard deviation (M±SD). Categorical and rank variables will be presented as percentages.
 
Statistical significance of differences between group for continuous variables will be evaluated with Student’s t-test after confirmation of normal variable distribution by Kolmogorov-Smirnov test.
 
For continuous variables with distribution other than normal Mann-Whitney U-test will be used. For comparison of the proportions Pearson chi-squared test will be performed.
 
Criterion of response to the treatment is defined as the reduction of ISI score reduction of >7 points from baseline. Remission criterion is defined as final ISI score of 7 points or less. Nonresponse criterion is defined as ISI score decrease of ≤7 points from baseline. Based on these dichotomic values participants will be divided into two groups: responders and nonresponders for each method of treatment.
 
Comparison of responders and nonresponders baseline quantitative characteristics will be performed using Student’s t-test (for normal data distribution) or Mann-Whitney U-test (for abnormal data distribution). Statistical significance will be set at a p-value less 0,05.

Rationale for Number of Subjects
	
Study design allows to compare two therapeutic approaches with a relatively small sample size and to determine the predictors of effectiveness for each treatment. Thus 40 patients get 2 therapeutic approaches. This is the representative sample size enough to produce normal variable distribution for further parameter statistical analysis.

PURPOSE OF THE INVESTIGATION

Name of investigational method

Brief behavioral therapy program
Imovan (zopiclone)

Intended use of the investigational method

2-week Brief behavioral therapy will be performed in two 1 hour session for treatment of chronic insomnia (CI)

Imovan (zopiclone) in a dose of 7,5 mg has to be taken 30 minutes before bedtime for two weeks

Overview of Clinical Studies

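### Predictor search: an assumed 32–56 tests at p<0.05 with no declared predictor list, multiplicity rule or exploratory label, and a responder split that cannot separate predictors from baseline severity

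*Combined protocol and SAP*

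**What the plan says.** Finding predictors of effectiveness for each method is the only secondary objective (Secondary Objectives), and Study Rationale ties it to individualised treatment.

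- Analysis of Secondary Endpoints: "participants will be divided into two groups: responders and nonresponders for each method of treatment". Then: "Comparison of responders and nonresponders baseline quantitative characteristics (polysomnographic, antropometric, psychometric) will be performed using" a t-test or, for non-normal data, a Mann-Whitney test. The threshold follows: "Statistical significance will be set at a p-value less 0,05".
- Synopsis, Primary Analysis Plan: the same comparison without the three families of variables ("Comparison of responders and nonresponders baseline quantitative characteristics will be performed using" the same two tests).
- Analysis of Primary Endpoint: "Criterion of response to the treatment is defined as the reduction of ISI score reduction of >7 points from baseline".
- Sample Size and Randomization, and the synopsis rationale for the number of subjects: the crossover design will allow the investigators "to determine the predictors of effectiveness for each treatment" with 40 patients.
- The variables appear elsewhere. The main polysomnographic (PSG) measures and the instruments are under Secondary Efficacy Endpoints, the questionnaires are also under Questionnaire and in Appendix 1, and "gender, age, height and weight" are under Demographic and Baseline Characteristics. None of these lists is declared to be the set of candidate predictors.
- Statistical Methods and Considerations refers to a SAP covering all analyses. The supplied text contains no multiplicity rule and does not call the predictor search exploratory.

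**The concern.** Many variables are each tested twice, once per method, at an unadjusted 5% level in a small sample. Some significant results are then expected even if nothing predicts response, and the plan has no rule for telling them from real ones. Because the search is presented as able to determine predictors and as a basis for individualised treatment, a chance finding could be read as guidance on choosing therapy.

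A second problem is independent of the number of tests. Response is defined by change from baseline, so baseline ISI is part of the outcome. Any characteristic that tracks baseline severity is drawn into the comparison, and a multiplicity correction alone does not address this.

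Third, separate tests within each method fit the stated objective, but they cannot show that a variable favours one method over the other, which is the clinical question in the synopsis rationale.

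**Working it through.** **The plan's own figure.** The sample size of 40 comes with no effect size, SD or power, so there is no calculation to reproduce.

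**Number of tests (assumed; baseline ISI left out because it is part of the outcome).**

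- Low: 5 named PSG measures + 1 sleep-stage measure + height and weight + 7 scores (BDI, two STAI parts, PSQI, DBAS, SHI, TAS-20) + 1 personality score = 16 variables; × 2 methods = 32 tests.
- Middle: 5 + 4 sleep stages + age, height and weight + 7 + 5 personality scores = 24; × 2 = 48 tests.
- High: add body mass index, the apnea–hypopnea and leg-movement indices (mentioned only as exclusion thresholds) and β-adrenoreactivity (outside the three named families) = 28; × 2 = 56 tests.

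**Expected chance findings if no predictor is real** = tests × 0.05, whatever the correlation between tests:

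- 32 × 0.05 = 1.6
- 48 × 0.05 = 2.4
- 56 × 0.05 = 2.8

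**Chance of at least one.** With independent tests:

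- 1 − 0.95^32 = 0.806
- 1 − 0.95^48 = 0.915
- 1 − 0.95^56 = 0.943

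Correlation lowers this. In null simulations with 40 patients and pairwise correlation 0.3–0.5, it was about 59–72% at 32 tests and 74–88% at 56. Over a wider set of correlation patterns the lowest values were 58% and 72%.

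**Coupling with baseline ISI.** Let B be baseline ISI, F final ISI, ρ their correlation, and assume equal SDs. The change B − F has correlation √((1 − ρ)/2) with B: 0.59 at ρ = 0.3, 0.50 at ρ = 0.5, 0.39 at ρ = 0.7. A variable correlated r with B, and with no further effect on F, has correlation r × √((1 − ρ)/2) with the change. At r = 0.5 that is 0.30, 0.25 and 0.19.

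Simulations of the responder split used n = 40 and assumed baseline mean 17, SD 5 or 7, mean fall 4–8 points and ρ 0.3–0.7. The SD of 7 matches the plan's remark that the threshold is about one pretreatment SD. Baseline ISI was significant in about 41–91% of trials. A variable correlated 0.5 with it was flagged in about 13–32%, against about 5% once baseline ISI was in the model.

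**Power at an assumed partial correlation of 0.4, n = 40.** For regression with two covariates, use Fisher's z: atanh(0.4) = 0.424; 0.424 × √(40 − 3 − 2) = 2.51.

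- At α = 0.05: Φ(2.51 − 1.96) ≈ 0.71 (simulated 0.72).
- At 0.05/48 = 0.00104: Φ(2.51 − 3.28) ≈ 0.22 (simulated 0.21).
- The planned split at more than 7 points, simulated with the predictor uncorrelated with baseline ISI: about 34–48% at 0.05.

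**Which baseline for the second course.** The synopsis requires patients to "fill in questionnaires prior and after the treatment", which for the second course could mean Visit 1 or Visit 3. Suppose a variable predicts BBT-I response only (r = 0.4) and that effect persists fully past the washout. With Visit 1 ISI as the only baseline, it appears as a false zopiclone predictor in about 24–25% of simulated trials. With the ISI measured before each course, the figure is 7–13%. At half persistence the figures are 10–11% and 6–7%.

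**The case against.** Four points on the other side have substance.

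- **The variables are listed.** A reader might infer that the plan leaves the predictors wholly undefined. It does not: three families are named, and the main measures and questionnaires appear in other sections. What is missing is a statement that these are the candidates, and at what level of detail (stage proportions, subscales, derived measures). The top of the 32–56 range depends on variables that the plan may never have meant to test.
- **Variables that track severity do predict response.** A reader might treat the 13–32% as a false-positive rate. That is not supported. The objective is to predict effectiveness, and such a variable does predict a fall of more than 7 points. The valid criticism is narrower: the plan cannot separate it from a variable that adds information beyond baseline severity.
- **Regression brings its own risk.** Under full persistence the planned split gives fewer false zopiclone predictors (about 5–8%, depending on the baseline used) than the regression with pre-course ISI (7–13%). Part of that reflects the split's lower power, but it is why the choice of baseline matters and why first-course estimates should be shown.
- **A SAP is mentioned.** The absence of a rule can be asserted only for the supplied text.

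The unadjusted 0.05 threshold, applied to every comparison under each method, remains.

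**Conclusion.** The concern holds. As written, the predictor analysis would be expected to yield about 1.6–2.8 significant tests by chance at an assumed 32–56 tests, if no predictor is real. These are tests, not distinct variables: one flagged under both methods counts twice. The chance of at least one is 81–94% only under independence, so those should not be quoted as the actual error rates; plausible correlation brings them down to roughly 58–72% at the lower end.

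The coupling with baseline ISI is a separate limit on interpretation and says nothing against the response definition itself. Its size rests on assumed ISI means, SDs and correlations, as the power figures rest on an assumed correlation of 0.4. Patients with only one completed course are admitted, so either analysis may have fewer than 40; that lowers power and leaves the expected chance count essentially unchanged.

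This should be corrected before analysis. It affects the secondary objective and how its results are read, not the primary comparison.

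**What to change.** In Analysis of Secondary Endpoints and the synopsis Primary Analysis Plan:

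1. Name the candidate predictors before analysis.
2. Apply Benjamini-Hochberg control at 5% across all within-method tests, report estimates with 95% confidence intervals, and label the results hypothesis-generating. In the two sample-size passages, speak of exploring possible predictors instead of determining them.
3. Keep the responder definition and comparison for description. Base inference on continuous end-of-course ISI regressed on the predictor, the ISI measured before that course (Visit 1 for the first, Visit 3 for the second) and sequence. Show first-course-only (Visit 2) estimates alongside. Do not use Visit 1 ISI as the only baseline for the second course.
4. Do not say that a predictor favours one method unless a treatment-by-predictor interaction, reported as exploratory, supports it.
5. Reconcile the Questionnaire section, which collects ISI at baseline and the next four visits, with Appendix 1, which has no ISI row. The regression depends on these scores.

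The cost is wording and ordinary regression, with no new visits if ISI is collected as the Questionnaire section says. The downside is fewer declared predictors: power at r = 0.4 is about 72% unadjusted and about 21% at the strictest of 48 steps. Interaction power is low. If a variable has r = 0.4 for BBT-I only, it is about 24% from first courses alone, and within-method BBT-I power in 20 first-course patients is about 41%. Carryover bias is reduced, not removed. In simulation the Benjamini-Hochberg rule kept the chance of any false predictor at about 4–5%, but only with no real predictors and no carryover.
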